6. STUDY PROCEDURES

Study Outline

Pre-screening Procedures:

During the pre-screening process, the subject can contact a co-investigator, usually via encrypted Zoom Enterprise call, and REDCap form. During the pre-screening process, the co-investigator will discuss the details of the study, explain the study procedures, and encourage the subject to ask questions. In the privacy of the encrypted Zoom Enterprise call for healthcare, the co-investigator will ask the subject questions from the following:

- 1) Online Screening questionnaire
- 2) Phone Pre-screening questionnaire

Once this information is collected, the co-investigator will consult with the PI regarding the eligibility of the subject, who will then give the approval for the subject to come to our laboratory for the screening procedure.

Visit 1

Online or in-person Screening and Consent Visit – (Approximate Time: 1 hour)

If in-person, the visit 1 can be performed together with the visit 2 - (Approximate Time: 3 hours and 30 min).

If done remotely; the documentation would be signed electronically, and the visit would be done by telephone or using Zoom Healthcare)

During the Screening, the PI and/or a co-investigator will conduct once more a review of inclusion/exclusion criteria to determine the subject's eligibility for enrollment. If the consent is conducted by the co-investigator, the PI will review and sign off. Study procedures will be reviewed with the subject, and documentation of informed consent will be obtained. We will use an encrypted web-based platform (REDCap e-consent module) via Zoom call (Enterprise plan). Both services are already validated and in use by the MGB network.

- Discuss study-specific procedures with the subject.
- Review inclusion and exclusion criteria.
- Obtain a signed and dated consent form.
- Conduct a Demographics Survey, Brief Medical History, Beck depression inventory (BDI), and the Edinburg Handness Inventory Short form (EHI/SF).

Visit 2

Baseline Visit and First taVNS session – (Approximate Time: 2 hours and 30 min).

Urine pregnancy exam (if applicable).

Baseline assessments:

- EEG
- HRV
- QST
- The Brief Mood Introspection Scale (BMIS)
- Visual Analogue Scale to Evaluate Fatigue Severity (VAS-F) adaptation using tiredness item.

After the Baseline assessments:

Subjects will receive one session of either active taVNS or sham taVNS for 60 min. During the stimulation both groups will also be assessed with EEG, HRV, and VAS-F.

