After the session, subjects will complete the following assessments:

- Side Effects Questionnaire for taVNS.
- Questionnaire to assess the success of blinding in clinical trials.
- EEG
- HRV
- QST
- BMIS
- VAS-F

Upon arrival and prior to the application, taVNS intensity will be measured for each participant separately, as above the detection threshold and below the pain threshold. The stimulation electrodes will be applied bilaterally to the ears, and in order to individually adjust the stimulation intensity, participants will receive increasing and decreasing series of 10-s stimulation trials and will rate the subjective sensation of the stimulation in a 10-point scale, ranging from nothing (0), light tingling (3), strong tingling (6), to painful (10). The increasing series of trials will start from an intensity of 0 mA and increase by 0.3 mA on a trial-by-trial basis until participants report it is uncomfortable to continue. This procedure will be repeated a second time. The final stimulation intensity for the experimental procedure will be calculated based on the average of the two intensities just below pain threshold.

We will use a Healaon Transcutaneous Auricular Vagus Nerve Stimulation (taVNS) device (Neurive Inc., Gimhae, South Korea), which consists of an earset, with conductive eartips placed on the auricular concha of the ears. Electrodes are connected to a stimulator, and during active stimulation, both the cyma conchae of the auricular are stimulated at 30Hz, 200-250 us, with adjustable intensity for 60 min. The sham intervention will be done at the same location bilaterally to the cyma conchae of the auricular, however the device will be off during the 60 min session.

Data for this study will be collected from subjects using an electronic format capture system (REDCap), and each subject will be assigned a de-identified code to collect the data. The data entered will be securely transferred to the Mass General Brigham REDCap database, to which only IRB-trained and approved study staff will have access. The following assessments will be performed:

Demographic data: This survey will ask about demographic characteristics, including age, gender, sex, race, ethnicity, educational level, hand dominance, weight, height, and body mass index.

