Medical history form: We will ask the history of medical conditions, a list of medications currently used, allergies, history of hospitalizations or visits to an emergency room in the last year, tobacco and alcohol consumption, and emergency and primary care physician contact.

BDI: This self-report inventory consists of 21 multiple-choice questions and is a widely used method to classify depression severity. It assesses the presence of several symptoms related to depression, such as irritability, hopelessness, and decreased cognitive performance. Physical symptoms such as weight loss and fatigue are also included.

EHI/SF: This short-form, self-report measure will be used to assess handedness in participants, asking their hand preference for 4 everyday tasks: writing, throwing, using a toothbrush, and using a spoon.

Eletroencephalogram: We will record the EEG using a 64-channel EGI system (Electrical Geodesics, Inc) (EGI, Eugene, USA) in resting and continuously during visual task stimulus presentation.

EEG phase synchronization of the DMN will be assessed in resting state with particular interest in the connectivity between mPFC to other brain regions in this network. EEG will be recorded using a high-density electrode array from two resting state conditions: eyes-open and eyes- closed. Oscillatory activity will be measured in the regional sources of interest that comprises nodes from the DMN, and phase synchrony between DMN regions of interest with reference to the medial prefrontal regions using phase-locking value (PLV). A data-driven statistical approach will be used to analyze the effects of taVNS on PLV. PLV, a measure of phase synchrony (i.e., the average of phase angle difference between two time series), can examine the synchronization in oscillatory activity between brain sources representative of the DMN (57). PLV can range from 0 to 1, with values close to 1 indicating strong synchronicity (i.e., perfect phase locking), while values close to 0 indicate substantial phase variation between the two signals, and thus low synchronicity between the two regions (i.e., no phase synchrony and randomly dispersed phases). To transform EEG data from scalp electrode space into source space, we will use a Matlab to model resting state activity representative of the DMN.

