The DMN resting state montage comprised six regional sources of interest: medial prefrontal cortex (mPFC), posterior cingulate cortex (PCC), left and right Angular Gyru (AG), and left and right lateral temporal cortices (LTC). As the multiple discrete sources approach is applied to source montages (58), activity from other brain areas can affect source waveforms of the DMN sources if only these DMN sources of interest are included in the source montage. Therefore, six additional noise sources were also included in the montage to measure brain activity that were not part of the networks associated with resting state activity in the DMN and to increase the sensitivity of the sources of interest. These noise sources comprised left and right occipital sources, left, right, and midline frontal sources, and a middle parietal source. To measure PLV, a complex demodulation method with 0.5 Hz wide frequency bins and 100 ms time resolution in the range of 1 to 50 Hz is used for decomposing the single-trial EEG data into 2-second time-frequency representations of temporal spectral evolution (TSE, an equivalent measure of oscillatory power) normalized to the power spectrum per participant. PLV will be measured from the radial component of each source of interest relative to the mPFC source as the seed (i.e., between mPFC and each of the sources at the PCC, left/right LTC, and left/right AG).

Functional connectivity: Fourier transformation (STFT) will be applied to filter the data into five typically analyzed frequency bands, delta (0.5–4 Hz), theta (4–8 Hz), alpha (8–13 Hz), beta (13–30 Hz) and gamma (30–80 Hz) bands, then we will apply the phase lag index (PLI) method to calculate the connectivity matrices and graph theory-based methods to measure the topology of brain networks across different frequency bands.

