Effects in pRR50	taVNS	Geng 2022 (cross-over) (20)	1.53 (0.67 to 2.37)	14 subjects	18 subjects (9 each group)
Effects in SDRR	taVNS	Geng 2022 (cross-over) (20)	2.79 (1.72 to 3.83)	6 subjects	8 subjects (4 each group)

Effects in total power	taVNS	Geng 2022 (cross-over) (20)	1.01 (0.22 to 1.80)	32 subjects	38 subjects (19 each group)
------------------------	-------	-----------------------------	---------------------	-------------	-----------------------------

AIM 1: Data forms and questionnaires will be coded in a standardized manner, and double-entered into our database. Digital measures/recording will be similarly tracked in our database and regularly backed up. Analyses will be conducted using standard statistical software such as STATA and MATLAB toolboxes. All analyses will be performed on an intention-to-treat basis (using the method of multiple imputations for missing data). We will also perform an additional sensitivity analysis using completers only. The primary outcomes for this aim will be the EEG biomarkers (alpha asymmetry, functional connectivity, and phase synchrony of the default mode network). We will obtain all the measurements at baseline and during the stimulation period. Linear mixed models will be used to test for differences between the active and sham group, adjusting for covariates when necessary. Further exploratory analysis to detect predictors of response to taVNS will be performed taking in consideration the covariates assessed. Statistical significance will be considered if p-values < 0.05.

The between subjects' factor and measures on hemisphere (left and right), and emotion (happy and sad) will be performed for alpha-1, alpha-2, and theta. All the power will be ln-transformed. The significant main effects will be further analyzed with Cohen's d effect sizes and the interactions will be divided in simple effect and graphical interpretations.

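### Aim 1's phase-locking cluster test covers 30 Hz on EEG taken while only the active arm is pulsed at 30 Hz, with no stated artefact rule and no post-session contrast; pick-up comparable to background could pass as a neural effect

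*Combined protocol and SAP*

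**What the plan says.** Section 9, Aim 1, lists three EEG primary outcomes: alpha asymmetry, functional connectivity and phase synchrony of the DMN. On timing it says "We will obtain all the measurements at baseline and during the stimulation period". Section 6 confirms the recording: "During the stimulation both groups will also be assessed with EEG, HRV, and VAS-F".

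Section 6 also sets the stimulation. In the active arm both ears are "stimulated at 30Hz, 200-250 us, with adjustable intensity for 60 min"; for sham, "however the device will be off during the 60 min session". Intensity is individual: "The final stimulation intensity for the experimental procedure will be calculated based on the average of the two intensities just below pain threshold".

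For PLV, Section 6 states: "A data-driven statistical approach will be used to analyze the effects of taVNS on PLV". The decomposition is "with 0.5 Hz wide frequency bins and 100 ms time resolution in the range of 1 to 50 Hz", with PLV taken between the medial prefrontal seed and five other DMN sources. Section 9 tests it with a permutation cluster test (cluster-forming alpha 0.01, 3000 permutations, 95% cluster threshold) between treatment groups, eyes open and closed. That paragraph names no time point.

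Post-session EEG is scheduled both in the visit table of Section 3 and in the after-session list of Section 6. Aim 2 uses an after-stimulation time point; Aim 1 does not mention one.

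**The concern.** Current from the stimulator that reaches several EEG sources at once adds the same 30 Hz oscillation to each. PLV measures how constant the phase difference between two sources is, so a shared oscillation raises it without any change in the brain. Here that signal would exist in one arm only and only during stimulation. Randomisation does not balance it, subtracting baseline does not remove it, and permuting arm labels cannot separate it from a treatment effect, because the arms really do differ at 30 Hz.

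The readable text names no stimulation-artefact step, excluded band or rule for a cluster at 30 Hz. Section 6 explains that the phase lag index rejects zero-lag coupling, but that protects the functional connectivity outcome; nothing similar is stated for PLV. The six extra noise sources are described as capturing other brain activity, not stimulator current. At stake is whether a positive result on a primary outcome of a mechanistic trial can be called neural.

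**Working it through.** **1. Is 30 Hz in the searched range?** Steps of 0.5 Hz from 1 to 50 Hz give (50 - 1)/0.5 + 1 = 99 grid points. 30 Hz is number (30 - 1)/0.5 + 1 = 59. Yes.

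**2. Arm size.** The plan's own figure reproduces. With d = 0.94, two-sided 5% and 80% power, 2 x (1.96 + 0.84)^2 / 0.94^2 = 17.7, so 18 per arm and 36 in total; 36 x 1.2 = 43.2, taken as 44, or 22 per arm. The checks below use 22 per arm.

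**3. Does shared pick-up raise PLV?** With no coupling, PLV over N epochs averages about sqrt(pi/(4N)). For an assumed N = 60 this is sqrt(3.1416/240) = 0.11. In simulation with no line, mean PLV at 30 Hz was 0.11-0.12. With even pick-up of 10% of EEG SD it was 0.54 (1.4 Hz filter) or 0.27 (4 Hz filter). Background at 30 Hz was 0.095 and 0.160 of EEG SD in those filters, so the line-to-background ratios are 0.10/0.095 = 1.05 and 0.10/0.160 = 0.63. A separate check at a nominal ratio of 1 gave a rise from about 0.11 to 0.29 (d about 1.4), and little change at low pick-up.

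**4. Does the cluster test then reject?** Three simulations, all with no neural effect, 22 per arm, five pairs, 1-50 Hz in 0.5 Hz bins, cluster-forming alpha 0.01 and 95% threshold. A: ten settings, change from baseline, 200 trials, 300 permutations. B: during-stimulation values, background coherence about 0.3, 100 trials, 200 permutations. C: uneven pick-up, change from baseline, 60 trials, 150 permutations. B was run on power ratios; amplitude ratio = sqrt(power ratio). Ratios in B and C are nominal.

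| Line/background amplitude at 30 Hz | A | B | C |
|---|---|---|---|
| 0 | 2.5-6% (0.2 or less) | 4-7% | 10% (same polarity) |
| about 0.3 | 3-85% | 2-11% | not run |
| 0.5-0.7 | 5-100% | 4-46% (0.5); 2-100% (0.71) | 10% (0.5, same polarity) |
| 1-1.5 | 9.5-100% | 71-100% (1); 100% (1.41) | same polarity 93-100%; random polarity 8-53% |
| 2 or more | 99-100% | 100% | random polarity 95% (2), 100% (3) |

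With 60 trials the standard error at 5% is sqrt(0.05 x 0.95/60) = 2.8 points, so the 10% cells in C are compatible with 5%. The ends of the table agree; the middle depends on polarity, evenness and filter width. One cell of A (ratio 0.05/0.160 = 0.31) gave 18% in one run and 43% in another.

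**5. Does leaving out a band help?** Dropping 27-33 Hz removes 13 of 99 grid points. The rate was then 2-11% in B with pick-up present, 2-8% in C, and 3-7% in A except one setting. There the line was 50% of EEG SD on a steep background with the 4 Hz filter, 0.50/0.058 = 8.6 times background, and the rate stayed at 100%.

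**6. Could pick-up be that large?** For a line of share s of EEG SD, a one-phase pulse of width w needs a scalp amplitude of s/(sqrt(2) x 30 x w). For s = 0.05 and w = 250 or 200 microseconds this is 4.7 or 5.9 EEG SD. A charge-balanced pulse divides by a further 2 x sin(pi x 30 x w), giving 100-156 with 200-250 microseconds per phase, or 400-625 if that width covers both phases. The documents do not say which pulse applies.

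**The case against.** The deciding quantity is missing. Pick-up size, polarity, pulse shape, epoch count and filter width are all assumptions, and the simulations add the line directly to the DMN sources. The actual montage also has six noise sources, which could absorb part of a stimulator field whatever their stated purpose; that leakage was not modelled. A well-balanced pulse might leave pick-up harmless. This stands: the table shows when the problem would occur, not how likely it is.

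The timing sentence in Aim 1 is loose. It conflicts with the scheduled post-session EEG, and Aim 2, described as similar, uses the later time point. A drafting omission is a fair reading. A reader might infer that no post-session EEG exists; the documents say the opposite. Likewise, an artefact procedure may sit in a processing manual, or in the part of the file that is unreadable after Aim 2.

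The trial is called exploratory, and a cluster confined to 30 Hz would be visible. True, but PLV is a named primary outcome, and without a rule such a cluster could be reported afterwards as either entrainment or artefact.

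A reader might also extend the point to all three EEG outcomes. The documents do not support that. Frontal asymmetry uses 4-13 Hz. The phase lag index rejects zero-lag coupling, and although 30 Hz is the edge of its beta and gamma bands, its network test was not simulated.

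**Conclusion.** The point holds for PLV, conditionally. As written, the only time points named in Aim 1 give a contrast in which 30 Hz pick-up is fully confounded with arm, and the search range includes 30 Hz. If pick-up reaching the DMN sources is comparable to or larger than the background EEG there, a significant cluster can arise with no neural effect; at about twice background or more, nearly all simulated trials gave one. If pick-up is small, the test stays near 5%.

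It would be wrong to conclude that the test has a known inflated error rate, or that contamination will occur: the documents do not give the pick-up, and the mid-range figures vary too much between models to quote as established. The uncertainty favours settling the reading rule before data are seen. This should be fixed but does not invalidate the design.

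**What to change.** In Section 9, Aim 1:

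1. Name the EEG time points as baseline, during and after stimulation. Prespecify for PLV the active-sham contrast of change from baseline to post-session EEG, reported beside the during-stimulation contrast as supporting evidence only. If it counted as a second route to a positive claim, two independent tests at 5% would give 1 - 0.95^2 = 9.75%.
2. Prespecify one sensitivity run of the during-stimulation PLV cluster test without a fixed band around 30 Hz, for example 27-33 Hz. Any widening should be judged on the active-minus-sham change in 30 Hz line power, with a stated upper limit. Active-arm power alone is not a safe guide: with an assumed broadband rise of 0.1 log units (SD 0.2), a rule widening wherever that power rose more than 5% removed nearly all of 1-50 Hz in 73% of simulated trials, against 2% when judged relative to sham.
3. State that a cluster that disappears in the masked run and is absent post-session will not be read as neural without other evidence.

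If an artefact procedure already exists, cite it here.

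The cost is wording and one extra analysis run, with no new visits or recordings. The masked run cannot assess true effects near 30 Hz: a simulated effect of d = 0.9 at 28-32 Hz was found in 100% / 98.5% of trials unmasked (1.4 / 4 Hz filter) and 4% / 5% masked. The same effect at 9-11 Hz was not harmed (100% / 93% unmasked, 100% / 93.5% masked). Effects that end with stimulation will not appear post-session, which is why that contrast should not act as a gate.
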